12.0 Data and Protocol Management

Data will be collected and entered in CORe by the research staff assigned to the study.

12.1 Good Clinical Practice

The conduct of the study will conform to the recommendations for clinical studies in human subjects as per the guidelines on "Good Clinical Practice", [21 CFR Part 312 and ICH guidelines].

13.0 Serious Adverse Events and Reporting Requirement

13.1 Adverse Events

An adverse event (AE) is any new, undesirable medical occurrence or change (worsening) of an existing condition in a subject that occurs during or after treatment, whether or not considered to be product related. Therefore, adverse events are treatment-emergent signs or symptoms.

For the purposes of this study, non-serious anemia (Hgb or Hct below the normal range or worsened from baseline) or iron deficiency (iron indices below the normal range or worsened from baseline) will not be considered adverse events. Anemia or iron deficiency will be considered end points if an intervention is required.

In this study, the following adverse effects are expected and will not be reported. They will be summarized in the updated and final analysis. Myelosuppression and its associated complications are part of the treatment of sarcoma. Therefore, low blood counts and related complications such as infections, bleeding and hospitalizations due to myelosuppression will not be reported as severe adverse drug reactions related to Injectafer.

AEs will be collected from the time of informed consent to 30 days after last study drug administration. AEs that occur before the first study drug administration, concomitant illnesses, which existed before study entry, but did not worsen during the treatment period and any pre-existing conditions are known as “pre-treatment AEs” and by definition are “unrelated” to study drug. All AEs, regardless of the source of identification (e.g., physical examination, laboratory assessment, electrocardiograms [ECG], reported by patient), must be documented.

Each AE will be assessed by the Investigator with regard to the intensity. Intensity should be assessed in accordance with the Common Terminology Criteria for Adverse Events (CTCAE v.4.03, Appendix C). Attribution of AE to study treatment will be recorded as follows:

Relationship (Causality): The Investigator will be asked to document his/her opinion of the relationship of the event to the study drug* as follows:

- **NONE** There is *no* evidence of any causal relationship.
- **UNLIKELY** There is *little* evidence to suggest there is a causal relationship. There is *another reasonable explanation* for the event (e.g., the subject's clinical condition, other concomitant treatments).
- **POSSIBLE** There is *some* evidence to suggest a causal relationship (i.e. there is a reasonable possibility that the adverse experience may have been caused by the agent). However, the influence of *other factors may have contributed* to the event (e.g., the subject's clinical condition, other concomitant events).
- **PROBABLE** There *is evidence* to suggest a causal relationship, and the influence of other factors is *unlikely*.

Timing: Non-serious AEs will be reported from the initial treatment with study drug* through the completion of the study. All ongoing adverse events related to study drug (i.e., Injectafer, ferrous sulfate) should be followed until they are no longer related, have taken a confounding medication or return to baseline grade.

* For the purposes of this trial, “study drug” is defined as: **Injectafer, oral iron supplement.**

Follow-up of Adverse Events

All AEs experienced by a patient, irrespective of the suspected causality, will be monitored until the AE has resolved, any abnormal laboratory values have returned to

baseline or stabilized at a level acceptable to the Investigator, until there is a satisfactory explanation for the changes observed, until the patient is lost to follow-up, or until the patient has expired.

For the purposes of this study, non-serious anemia (Hgb or Hct below the normal range or worsened from baseline) or iron deficiency (iron indices below the normal range or worsened from baseline) will not be considered adverse events. Anemia or iron deficiency will be considered end points if an intervention is required.

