9.0 Criteria for Response

9.1 Response

All patients who receive one dose of study drugs under this protocol will be evaluable for toxicity. All patients randomized will be considered evaluable for response in the intent-to-treat analysis.

Efficacy assessments will include:

- Hemoglobin, TSAT, and other iron panel test measures
- Patient reported outcomes questionnaires (FACT-Fatigue)
- The use (or lack of use) of other therapies for anemia (eg, RBC or whole blood transfusions, ESA, or both)

9.2 Response will be defined as proportion of achieving an increase in hemoglobin at any time from baseline to end of 3 months, as described below:

Complete response (CR): increase in HGB ≥ 2.0 g/dL above baseline, and/ or
transfusion free.

Partial response (PR): increase in HGB (≥ 1 g/dL- 2 g/dL) above baseline

Minor response (MR): increase in HGB (≥ 0.5 g/dL- 1 g/dL) above baseline

9.3 Toxicity: Toxicities will be graded using the Common Terminology Criteria for Adverse Events v4.03 – CTCAE (see Appendix C). Uncomplicated, severe, or life threatening neutropenia and thrombocytopenia are expected toxicities of the systemic therapy and as such will not be collected as adverse events in this study since the data is already captured through the CORe.

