13.2 Serious Adverse Events

Definition: An adverse event is classified as SERIOUS if it meets any one of the following criteria:

- **Death**
- **Life-Threatening:** The subject was at substantial risk of dying at the time of the adverse event or it is suspected that the use / continued use of the product would result in the subject's death.
- **Hospitalization (initial or prolonged):** Required admission to the hospital or prolongation of a hospital stay.
- **Disability:** Resulted in a significant, persistent, or permanent change, impairment, damage or disruption in the subject's body function/structure, physical activities or quality of life.
- **Congenital Anomaly/Birth Defect**
- **Important medical events:** Other medically important events that, in the opinion of the investigator, may jeopardize the subject or may require intervention to prevent one of the other outcomes listed above.

A distinction should be drawn between SAE and severe AE. A severe AE is a major experience of its type. A severe AE is not necessarily serious: e.g. nausea, which persists for several hours, may be considered severe nausea, but it is not an SAE. On the other hand, a stroke, which results in only a limited degree of disability may be considered a mild stroke, but would be a SAE.

Timing: SAEs as well as AEs will be elicited during study visits and contact with subject. These AEs/SAEs as well as SAEs discovered through passive reporting from the time of initial treatment with study drug up to the completion of the study will be reported. Hospitalizations resulting from historical conditions (present prior to initial treatment with study drug or prescheduled prior to treatment with study drug) that have not increased in severity or led to prolongation of hospital stay should not be considered SAEs. All reported serious adverse events should be followed until they are no longer serious, or return to baseline grade.

Reporting: Any SAE, starting with the first dose of study drug, that is to be reported (as outlined in Timing section above) must be reported immediately (by the end of the next business day) to Luitpold Pharmaceuticals, Inc. by telephone, email and/or fax of the written SAE report form to the contacts listed below:

Safety Monitor
Luitpold Pharmaceuticals, Inc.
[contact]
[contact] [contact]

All serious adverse events will be reported to the University of Texas M.D. Anderson Cancer Center IRB within 24 hours of knowledge of the event.

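### Section 13.1 tells sites not to report hospitalizations due to myelosuppression, Section 13.2 makes them reportable SAEs, and the attribution exemption names only one of the two study drugs

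*Combined protocol and SAP*

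**What the plan says.** Section 13.1 opens its exemption without naming a drug or an arm: "the following adverse effects are expected and will not be reported. They will be summarized in the updated and final analysis". It gives the reason, "Myelosuppression and its associated complications are part of the treatment of sarcoma", and concludes, for cytopenias and their consequences, that "infections, bleeding and hospitalizations due to myelosuppression will not be reported as severe adverse drug reactions related to Injectafer". The same section requires every AE to be documented whatever its source, and asks the investigator to grade its relationship to study drug on a four-level scale. It defines study drug as "Injectafer, oral iron supplement".

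Section 13.2 lists hospitalization as a seriousness criterion: "Required admission to the hospital or prolongation of a hospital stay". The only admissions it exempts are those for historical or prescheduled conditions that have not worsened or prolonged a stay. On reporting, it begins "All serious adverse events will be reported to" the IRB, within 24 hours, and it gives the manufacturer until the end of the next business day.

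Section 9.3 has a related exclusion, again with no arm named: neutropenia and thrombocytopenia "will not be collected as adverse events in this study since the data is already captured through the CORe". Section 11.0 plans toxicity frequency tables overall and by arm for everyone who received one dose.

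**The concern.** Two things are at stake. The first is patient safety. An admission for an infection or a bleed attributed to myelosuppression falls under 13.1, which says not to report it, and under 13.2, which says to report it urgently. Site staff have no stated rule for choosing between them.

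The second is the comparison of toxicity between arms, which serves secondary objective 1. The sentence that withholds the drug-reaction label covers one of the two study drugs. The trial is open label, so whoever decides whether an event was due to myelosuppression, and whether it was related to study drug, knows the arm.

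**Working it through.** The plan gives no figure for this point. Its one design calculation, 93% power for the complete-response comparison, reproduces (93.3% with the pooled-variance formula) but concerns efficacy and is not used here. The check is mainly a comparison of text.

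**1. Is there a conflict on reporting?**

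| Question | Section 13.1 | Section 13.2 |
|---|---|---|
| Is an admission due to myelosuppression covered? | Yes, hospitalizations are listed | Yes, any required admission or prolonged stay |
| Is it reported? | The lead-in says no | Yes, to the IRB and the manufacturer |
| Is there an exception? | None referring to SAEs | Only historical or prescheduled conditions that have not worsened |
| Does attribution matter? | The last sentence concerns Injectafer-related severe reactions | No attribution condition |

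Section 13.2 distinguishes severe from serious, so the last sentence of 13.1 might be read as touching only severe reactions. That does not remove the conflict. The lead-in, "In this study, the following adverse effects are expected and will not be reported", is not limited to severe events, and the list names hospitalizations, which 13.2 makes serious by definition.

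**2. Does the attribution sentence treat the arms alike?** Study drug covers both agents, and the four-level scale applies to both. The sentence withholding attribution names Injectafer only, with no counterpart for oral iron. By contrast, the lead-in and Section 9.3 name no arm. The asymmetry is therefore confined to the labelling of severe reactions as drug-related.

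**3. How large could the effect be?** Let p be the true rate of these events, assumed equal in both arms, and let a be the share of Arm B events that the investigator attributes to oral iron. Arm A shows none, by rule. In a table of related severe reactions:

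gap = p × a, and the expected Arm B count = 25 × p × a (assuming all 25 per arm are treated).

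The documents give neither p nor a. With assumed values:

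| Assumed p | a = 0 | a = 0.5 | a = 1 |
|---|---|---|---|
| 5% | 0 | 2.5 points | 5 points (0 vs 1.25 patients) |
| 10% | 0 | 5 points | 10 points (0 vs 2.5) |
| 20% | 0 | 10 points | 20 points (0 vs 5) |
| 30% | 0 | 15 points | 30 points (0 vs 7.5) |

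The last column only restates the assumed rate. In a table of all such events regardless of attribution, the gap is p − p = 0.

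**4. Is the data source for the promised summary clear?** For cytopenias it is: Section 7.0 requires at least weekly CBCs for 3 months, and 9.3 says CORe holds the data. Blood counts cannot show infections, bleeds or admissions, so their summary depends on the rule in 13.1 that all AEs be documented. That sits awkwardly beside an instruction not to report them.

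**5. Does the stated reason fit?** Section 13.1 refers to the treatment of sarcoma. Section 5.2 gives the background treatment as TKI-based therapy for GIST.

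**The case against.** The strongest reply is that nothing is lost. Section 13.1 keeps these effects in the final summary and requires all AEs to be documented. Section 7.0 adds a daily symptom diary for 3 months, and Section 14.0 has SAEs submitted to the IRB and entered in CORe. On this view the attribution sentence merely declines to blame the study drug for an expected effect of background therapy. Only complications due to myelosuppression are covered, so tumour bleeding remains reportable.

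Much of this stands. Sections 9.3 and 13.1 can both hold for cytopenias, and the by-arm tables are not restricted to related events.

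A reader might infer that the carve-out biases the trial's toxicity comparison toward Arm A, for example by turning 5 events in each arm into 0/25 versus 5/25 drug-related (two-sided Fisher p = 2 × 53,130 / 2,118,760 = 0.0502). The documents do not support that. It needs an assumed 20% rate, a related-only table that the plan does not specify, and an investigator who attributes every Arm B event to oral iron. The last is implausible on the protocol's own scale, where another reasonable explanation, such as concomitant treatment, points to an unlikely relationship.

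The reply does not answer the reporting conflict. A summary at the end of the trial does not replace notice within 24 hours, and 13.1 does not say that 13.2 prevails.

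**Conclusion.** The reporting conflict is real. Sections 13.1 and 13.2 give opposite instructions for hospitalizations due to myelosuppression, and following 13.1 could keep serious events out of expedited reporting. This rests on the wording alone and needs no assumption about event rates. The documents do not show that any event would in fact be withheld.

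The one-sided attribution wording is also real, but its consequence is limited. It could tilt a table of drug-attributed severe reactions in favour of Arm A, by an amount that cannot be computed from the documents. Bias in the planned all-cause tables is not shown: the effect there is nil provided the events are collected and summarized as stated. The sarcoma wording is a smaller matter, but it is the stated reason for the exemption and should describe this trial. The changes should be made.

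**What to change.** - **Sections 13.1 and 13.2:** reconcile them by stating in 13.1 that any event meeting the criteria in 13.2 is reported as an SAE in either arm, whatever its suspected cause.
- **Attribution:** apply one rule to both arms. Either replace Injectafer with study drug in the exempting sentence, or delete that sentence and rely on the four-level scale.
- **Section 11.0:** state that infections, bleeding and hospitalizations due to myelosuppression are tabulated by arm regardless of attribution.
- **Section 9.3:** state that neutropenia and thrombocytopenia are graded by CTCAE from the weekly CBCs and tabulated by arm.
- **Rationale:** reconcile the reference to sarcoma with TKI-treated GIST.

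The cost is an amendment to the wording and a few more SAE forms. No new assessments are needed.

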7.0 Evaluation During Study

- Interim History and Physical examination including weight will be done before and after 3 months of the initiation of treatment.
- CBC differential and platelet counts will be monitored at least once a week for 3 months.
- Serum electrolytes and chemistries will be performed prior to and as frequently as needed during the treatment.
- Serum iron, serum ferritin, and total iron binding capacity (TIBC), and percentage serum transferrin saturation (TSAT) will be done at baseline, and every month for 3 months and then at 6 months.
- Patients will report the FACT-Fatigue and energy score at baseline and every month for 3 months and then at 6 months. In addition, patients will continue to report on daily symptom record diary the adverse events for 3 months [24].
- Management of hypersensitivity to the study drug: Patients with allergic reactions can be symptomatically managed. All patients with grade 4 hypersensitivity reactions (anaphylaxis) will be removed from the study.

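### The protocol gives conflicting end dates for AE collection, and the toxicity tables name none; the explicit 30-day rule would observe Arm B up to 3.3 times as long as Arm A

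*Combined protocol and SAP*

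**What the plan says.** Three places set an end to AE capture, and they differ.

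- **Section 13.1, collection rule:** "AEs will be collected from the time of informed consent to 30 days after last study drug administration". The same section adds: "All AEs, regardless of the source of identification (e.g., physical examination, laboratory assessment, electrocardiograms [ECG], reported by patient), must be documented".
- **Section 13.1, Timing:** "Non-serious AEs will be reported from the initial treatment with study drug* through the completion of the study". The footnote there defines study drug as Injectafer or the oral iron supplement. Section 13.2 likewise says that AEs and SAEs "from the time of initial treatment with study drug up to the completion of the study will be reported".
- **Section 7.0:** "patients will continue to report on daily symptom record diary the adverse events for 3 months". The repeat examination is also tied to 3 months: "Interim History and Physical examination including weight will be done before and after 3 months of the initiation of treatment". Other assessments continue longer: "Patients will report the FACT-Fatigue and energy score at baseline and every month for 3 months and then at 6 months". Iron indices follow that same schedule.

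Study completion is not defined for AE purposes. Section 8.0 lists end-of-study evaluations but gives no date.

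Section 11.0 plans toxicity frequency tables, overall and by arm, for everyone who received one dose. It states neither a time window nor an exposure adjustment. Section 5.1 gives Arm A two infusions 7 days apart and Arm B daily oral iron for 3 months.

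**The concern.** A new non-serious AE on day 60 in Arm A is outside the section 13.1 collection rule but inside the section 7.0 diary. It is also inside the reporting rules of sections 13.1 and 13.2, whether completion means 3 or 6 months. Site staff cannot tell whether to record it, and the analyst cannot tell whether to count it.

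The choice matters because toxicity is secondary objective 1 and is to be shown by arm. The collection rule is tied to last dose, and the planned dosing spans are about 1 week and about 3 months, so that rule observes the arms for very different lengths of time. Both arms have background TKI therapy. Events that build up over time, whatever the iron product, would have less time to appear in Arm A, and a simple frequency table would then favour Injectafer at equal toxicity.

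**Working it through.** The documents state no AE window length by arm, so there is no figure of the plan's own to reproduce on this point.

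**Inputs.** First dose = day 0. Last Injectafer dose = day 7 and last oral dose = about day 91 with full adherence (section 5.1; 3 months taken as 91 days, 6 months as 182). Tail = 30 days (section 13.1). 25 patients per arm (section 5.1).

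**Scheduled days observed from first dose**

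| Rule | Arm A | Arm B | Ratio B/A |
|---|---|---|---|
| Section 7.0 diary, 3 months | 91 | 91 | 1.0 |
| Sections 13.1 Timing and 13.2, completion read as 3 months | 91 | 91 | 1.0 |
| The same, completion read as 6 months | 182 | 182 | 1.0 |
| Section 13.1 collection rule, last dose + 30 | 7 + 30 = 37 | up to 91 + 30 = 121 | up to 121/37 = 3.3 |

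Taking 3 months as 84 to 92 days gives 114 to 122 days in Arm B and a ratio of 3.1 to 3.3.

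**Size under the collection rule**

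- Patient-days: 25 × 37 = 925 against up to 25 × 121 = 3,025.
- Share of the 6-month schedule: 37/182 = 20% against up to 121/182 = 66%.
- Arm A diary days after collection stops: 91 − 37 = 54 of 91, or 59%.

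**Early stopping of oral iron.** Section 5.3 lets intolerant Arm B patients leave the protocol. Assume a fraction f stops at day 14, so that their window is 14 + 30 = 44 days. The Arm B mean is (1 − f) × 121 + f × 44:

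- f = 0%: 121 days, ratio 3.3.
- f = 40%: 72.6 + 17.6 = 90.2 days, ratio 2.4.
- f = 100%: 44 days, ratio 1.2.

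**Illustration only.** Assume the same constant event rate in both arms, full adherence, and P(at least one event) = 1 − exp(−rate × days/30.4). The documents give no such rate.

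| Assumed rate per patient-month | Arm A, 37 days | Arm B, 121 days | Either arm, 91 days |
|---|---|---|---|
| 0.1 | 11% | 33% | 26% |
| 0.3 | 31% | 70% | 59% |

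The difference between the arms in this table comes from window length alone.

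**The case against.** The strongest reply is that the harm is conditional. It arises only if the 30-day rule governs; the other rules give equal scheduled windows. Sites could satisfy every section by collecting over the longest period. Contact is similar in both arms well past day 37, with the diary and at least weekly blood counts for 3 months. All of this is true and limits the point. But visits and blood counts do not set an end date for new AEs, and nothing says which rule the tables follow. Nor does separating collection from reporting resolve the conflict, since an AE that was never collected cannot be reported. The requirement to document all AEs concerns how an event is found, and follow-up to resolution concerns events already identified. Neither sets the end date for new events.

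Second, the events most specific to Injectafer are safe under every reading. Section 2.4.2 puts the largest phosphorus fall at Day 14, inside even the 37-day window. This stands: what is exposed is later-onset events.

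Third, the affected events are fewer than all AEs. Section 9.3 says neutropenia and thrombocytopenia "as such will not be collected as adverse events in this study since the data is already captured through the CORe", and section 13.1 does not count non-serious anemia. Section 13.1 also handles complications of myelosuppression separately, including infections and bleeding, and says expected effects will be summarised at analysis. The concern is therefore mainly with other, non-haematologic events.

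Finally, the illustrative percentages rest on assumed rates and a constant hazard, which early oral-iron intolerance or infusion reactions would not follow. That is fair; the window lengths make the case without them.

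**Conclusion.** The concern holds. The plan is wrong as written: an explicit collection rule contradicts the reporting rules and the diary, and the toxicity analysis does not choose between them. If the section 13.1 collection rule governs, scheduled observation is about 37 days in Arm A against up to 121 in Arm B. That assumes full planned dosing and 91 days for 3 months; early stopping of oral iron brings the ratio down from 3.3, to 1.2 in the extreme case shown. If one of the other rules governs, the scheduled windows are equal, provided study completion is a single time point for both arms.

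The effect is confined to the descriptive safety comparison. The primary CR analysis and its power are untouched. The correction should be made before toxicity is tabulated, because Arm A events not captured after day 37 may not be fully recoverable later.

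**What to change.** - Reconcile sections 7.0, 13.1 and 13.2 so that AE capture has one stated end, and define study completion as the 3-month or the 6-month assessment.
- In section 11.0, state one tabulation window from first dose, identical in both arms whatever the date of last dose. For AEs, first dose to the 3-month visit fits the existing diary and examination; a window to a defined study completion would also be equal.
- Tabulate SAEs over a common window to study completion, as section 13.2 already reports them.
- List events between consent and first dose, and any others outside the window, separately.
- State that Arm B patients who leave the protocol for standard-of-care IV iron (section 5.3) keep AE follow-up as section 10.1 provides after treatment discontinuation, with events after that IV iron flagged.

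**Cost.** A wording amendment. If the 30-day rule had been followed, AE capture in Arm A extends by 54 days (day 37 to day 91), which the existing diary and 3-month examination support. With a 3-month AE window, up to 121 − 91 = 30 days of Arm B events move from the main table to a listing.
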